### 13 **Procedures to minimize risk**

- As outlined above, this study will be an exploratory phase 2 trial of a combination of romidepsin and 3BNC117 in humans. Potential trial volunteers will be informed

about the possible risks of the monoclonal antibody administration and that there may be unknown risks.

- In the US, medical records and routine laboratory data will be handled with HIPAA compliance. Medical records will be protected by the rules and regulations of RUH, AUH and UCH.
- With any new medicine or monoclonal antibody, there is a possibility of totally unexpected side effects. Subjects will be monitored for 1 hour post 3BNC117 or romidepsin infusions in the site infusion unit. The study site infusion units are equipped for providing emergency medical interventions in the unlikely event of acute allergic or other reactions. In case of an emergency, after stabilization of the subject, he/she will be transferred to a tertiary care center, for specialized medical care.
- Subjects will be closely monitored for the development of symptoms of ocular disease (such as blurry vision, increased lacrimation, redness, dryness, pain). If subjects develop symptoms or signs of ocular disease, they will be referred to an ophthalmologist for diagnosis and management. These evaluations will be performed at no cost to the subject.
- During the treatment interruption phase of the study, plasma HIV-1 RNA levels will be monitored weekly and CD4+ T cell counts will be monitored every 2 weeks. ART regimen will be resumed if plasma HIV-1 RNA level is  $\geq 200$  copies/ml in 2 consecutive measurements or if CD4+ is found to be  $< 350$  cells/ $\mu$ l on two consecutive measurements, the participant becomes pregnant, or if otherwise clinically indicated.
- In order to minimize the risk of transmitting HIV to their partners if subjects become viremic, and of HIV-1 superinfection from an HIV-infected partner, subjects will be asked to use male or female condoms for the duration of ART interruption. In the event of a high-risk exposure to an HIV-infected partner, a subject may re-initiate ART as clinically indicated by his/her primary care physician.
- To minimize risks associated with phlebotomy, blood drawing will be performed by experienced phlebotomists. Should discomfort occur, they will provide appropriate treatment.
- To minimize risks associated with blood drawing, volunteers will be closely monitored for signs and symptoms of anemia.
- Females of childbearing potential and who participate in sexual activity that might lead to pregnancy will be advised to use two reliable forms of contraception (i.e. condom with spermicide, diaphragm with spermicide, progestin-only containing intrauterine device (IUD) (eg, Mirena, Implanon, Nuva Ring), non-estrogen containing formulations of hormonal birth control drugs with condom) for the study

duration. Romidepsin may interact with estrogen-based contraceptives and such agents may be unreliable in participants receiving romidepsin.

- In addition, a pregnancy test will be performed at screening, on the days of drug infusion, and throughout the course of the study. Males who are not anatomically sterile and who participate in sexual activity that might lead to pregnancy will be advised to use two reliable forms of contraception during the study to avoid pregnancy in a spouse or partner.
- Subjects will have regularly scheduled visits to the outpatient clinic and routine safety laboratories will be checked according to the Time of Events Schedule (Appendix A). HIV-infected individuals will have close monitoring of HIV-1 viral load and CD4 counts according to the Time of Events Schedule (Appendix A).
- In view of potential ECG changes associated with romidepsin, ECGs will be performed as described above (section 6.2.4). Serum potassium, magnesium and calcium will also be checked before each infusion. Any emergent ECG findings, including asymptomatic findings, will be assessed by a cardiologist and appropriate monitoring and/or management will be instituted as clinically indicated.
- Participants will be counseled during the informed consent process regarding the possible effects on fertility that may occur as a result of romidepsin. If requested, participants will be given information on centers where sperm or egg banking could be performed.
- Infusion-related adverse events including cytokine release syndromes will be monitored and graded using the CTCAE v4.03 grading scale ; all non-infusion-related adverse events will be graded using the DAIDS Table for Grading the Severity of Adult and Pediatric Adverse Events, Version 2.0 (Appendix C).
- Adverse events will be managed by the study site investigators who will assess and treat the event as appropriate, including referral to an independent physician and/or department. Participants who develop graded elevations in total bilirubin will undergo a diagnostic workup at no cost to the participant that includes right upper quadrant ultrasound, testing for gamma glutamyl transferase (GGT), HAV, HBV, HCV, EBV, CMV, VZV and HSV serologies, and any other relevant laboratory tests as determined by the investigators.
- Safety monitoring at each clinical site will be conducted by an external monitor and by an external Study Monitoring Committee (SMC). The RUH, AUH and UCH IRBs will conduct the initial review of the proposed study and will follow progress through annual reports and by immediate notification of serious and unanticipated adverse events. Any serious adverse events will be reviewed by the study investigators immediately. Site investigators will notify the local IRB and the sponsor at the Rockefeller University within 2 working days from the investigators being made aware of the event. The RU sponsor will notify the FDA, Danish Health Authority,

PEI, and BfArm per 21 CFR 312. The SMC will be available to the investigators for consultation and review of severe adverse events if needed.

#### **14 Alternative methods or treatments**

This does not apply to this study.

#### **15 Data and Safety Monitoring Plan**

This is an exploratory Phase II study, which exposes the subjects to “moderate risk.”

##### **15.1 Protocol Safety Review Team**

The Protocol Safety Review Team (PSRT) will include the available site PIs and co-investigators. Additional members could include senior clinical research nursing staff and site staff. The PSRT will meet on a weekly basis to review any adverse events; minutes will be recorded. For any AE Grade 3 or above deemed possibly, probably or definitely related to 3BNC117 and/or romidepsin, the site PI will notify the PSRT within 24 hours and the PSRT will convene within 1 business day to review these AEs. The PSRT will decide by consensus whether AEs should also be reviewed by the SMC.

All available safety data will be reviewed by the SMC three weeks after the first five participants receive the second 3BNC117 infusion, and every 6 months thereafter. The study will not pause, but following the review, SMC member(s) will make a recommendation to the principal investigator(s) regarding the continuation of the trial.

SAEs and unanticipated adverse events will be reported to the SMC within 2 working days of the site becoming aware of the event. If there is one grade 4 SAE judged as possibly, probably or definitely related to the administration of 3BNC117 or romidepsin by the principal investigator or designee, no additional enrollment will take place pending a review by at least two members of the SMC. Following this review, the SMC member(s) will make a recommendation to the principal investigator regarding the continuation of the trial.

All updated versions of the protocol will be provided to the SMC members. The review of trial data by the SMC will take place at least every 6 months. For these reviews, the study team will provide the SMC with updated records of all adverse events (AEs) of a grade 2 or greater toxicity.

The SMC will provide a written report to the sponsor at the RU and the site PIs after each evaluation. The PIs will, in turn, distribute these reports to the study team, the local IRBs and the FDA.

### 15.3 Monitoring

Safety monitoring at both sites will be conducted by the study investigators and by an external monitor. External monitoring reports will be reviewed and approved by the Sponsor. An external SMC will review SAE's and Unanticipated AEs and will be available to the study investigators for consultation. The RU, AU and UC IRBs will conduct the initial review of the proposed study and will follow progress through annual reports and by immediate notification of SAEs and UAEs. External monitoring will occur at least quarterly at all clinical sites.

### 15.4 Adverse Event Classification

The CTCAE v4.03 grading scale and DAIDS Table for Grading the Severity of Adult and Pediatric Adverse Events, Version 2.0 will be used for all occurring adverse events (Appendix C). Serious adverse events are defined as those that result in death, are life threatening, require inpatient hospitalization, result in significant disability or incapacity, is a congenital anomaly or birth defect, or is judged by the investigators to be a significant medical event.

### 15.5 Reporting Adverse Events

All adverse events will be reported to the local IRBs at least annually. Serious Adverse Events, (SAEs) will be reported to the local IRBs and to the sponsor at the Rockefeller University according to policy, within two working days of identification of the SAE. The RU sponsor will report SAEs directly to the FDA, Danish Health Authority, PEI, and BfArm per 21 CFR 312 (Appendix G).

### Expedited Reporting by Investigator to Celgene

Serious adverse events (SAE) are defined above. The investigator must inform Celgene in writing using a Celgene SAE form or MEDWATCH 3500A form of any SAE within 24 hours of being aware of the event. The written report must be completed and supplied to Celgene by facsimile within 24 hours/1 business day. The initial report must be as complete as possible, including an assessment of the causal relationship between the event and the investigational product(s), if available. Information not available at the time of the initial report (e.g., an end date for the adverse event or laboratory values received after the report) must be documented on a follow-up report. A final report to document resolution of the SAE is required. The Celgene tracking number (RV-XX-PI-###) and the institutional protocol number should be included on SAE reports (or on the fax cover letter) sent to Celgene. A copy of the fax transmission confirmation of the SAE report to Celgene should be attached to the SAE and retained with the patient records.

### **15.6 Reporting Unanticipated AEs**

Unanticipated Adverse Events (UAEs) will be reported to the local IRBs. UAEs that are related and greater than moderate severity must be reported to the local IRBs and to the sponsor at the Rockefeller University according to policy, within two working days of identification of the UAE. The RU sponsor will report UAEs to the FDA, Danish Health Authority, PEI, and BfArm per 21 CFR 312.

### **15.7 Clinical Laboratory Improvement Amendment/Clinical Laboratory Evaluation Program (CLIA/CLEP)**

This study includes tests that are not CLIA/CLEP certified. The results of such tests will not be used in clinical decision-making or shared with subjects or their health care providers.

### **15.8 Study Pausing Rules**

If the trial is placed on safety pause, all enrollment and infusions will be suspended pending review. The AEs that may lead to a safety pause or prompt PSRT AE review are summarized in Table 1.

**Table 1 Adverse events that may lead to a safety pause**

Event and relationship to study product	Severity	Occurrence	Action
SAE, related	Grade 3 or 4	First	Immediate pause until PSRT and SMC determination to resume enrollment
AE  , related	Grade 3 or 4 	Second 	Immediate pause until PSRT and SMC determination to resume enrollment
ALT or AST increase > 3 x ULN with concurrent increase in total bilirubin > 2 x ULN, any relatedness	N/A	First	PSRT and SMC review to consider pause
Abnormality of ANC, platelet count, or hemoglobin, any relatedness	Grade 4	First	PSRT and SMC review to consider pause
AE  , related	Grade 3 or 4 	First	PSRT review within 1 business day to consider pause

 Does not include subjective solicited symptoms (fatigue/malaise, myalgia, arthralgia, chills, headache, nausea).

 If no evidence of disease is present other than an abnormal laboratory value, the test must be repeated at least one time.

 PSRT and SMC will determine whether the reported related AE (Grade 3 or 4) is a second occurrence of a previously reported AE (Grade 3 or 4).

If a study pause is triggered, all enrollment and infusions will be held until review by the PSRT or SMC. Resumption of enrollment and study treatment may be determined by the PSRT or SMC (in consultation with the FDA, if required) following a cumulative review of the available safety data as outlined in the charter. If a decision to resume study enrollment and study treatment administration is made, the PSRT and/or SMC will record its judgment. As needed, the appropriate regulatory authorities will be informed in writing of the decision by the PSRT and/or SMC to resume or discontinue study activities. Sites are responsible for notifying their IRBs according to local standards and regulations.

Volunteers will be withdrawn from the study if: a) the study team feels that continued participation in the study would be harmful to the health of a subject; b) if the study volunteer fails to comply with the study procedures and/or fails to keep study visit

appointments; c) The RU, AU or UC IRBs decided to stop or cancel the study for any reason.

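### Section 15.8 gives two rules for lifting an automatic safety pause: Table 1 rows 1 and 2 require the PSRT and the SMC, but the paragraph below accepts either one

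*Combined protocol and SAP*

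**What the plan says.** Section 15.8 opens by defining what a safety pause does: "all enrollment and infusions will be suspended pending review". Table 1 then lists five triggers.

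- Rows 1 and 2 are the only automatic pauses. Row 1 is a first related SAE of grade 3 or 4; row 2 is a second related AE of grade 3 or 4. Both carry the same action: "Immediate pause until PSRT and SMC determination to resume enrollment".
- Rows 3 and 4 (combined liver abnormality; grade 4 blood count abnormality) call for "PSRT and SMC review to consider pause".
- Row 5 (first related AE of grade 3 or 4) calls for "PSRT review within 1 business day to consider pause".

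The paragraph under the table does not distinguish between rows. Once a pause is triggered, "all enrollment and infusions will be held until review by the PSRT or SMC". It continues: "Resumption of enrollment and study treatment may be determined by the PSRT or SMC", with FDA consultation if required and a cumulative safety review as set out in a charter.

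Section 15.1 makes up the PSRT from available site principal investigators and co-investigators, with possible additions from nursing and site staff. Sections 13 and 15.3 describe the SMC as external.

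**The concern.** Rows 1 and 2 require two bodies to agree before the trial resumes. The paragraph requires one, and does not say which. The two bodies are not interchangeable: one is the team running this open-label trial, the other is outside it. A site that follows the paragraph could treat the PSRT's decision as sufficient; a site that follows the table could not.

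The conflict falls on the two most serious triggers. Section 12 states that 3BNC117 and romidepsin have not been given together before, so these are the events after which external agreement matters most. Whether that agreement is needed should not depend on which sentence of section 15.8 is read.

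**Working it through.** No arithmetic applies. The check compares the wording on one question only, who ends a pause, and then looks for text elsewhere that would settle it.

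**Step 1: the statements on who ends a pause**

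| Place in section 15.8 | Pause covered | Who ends it |
|---|---|---|
| Table 1, row 1 | First related SAE, grade 3 or 4 | PSRT and SMC |
| Table 1, row 2 | Second related AE, grade 3 or 4 | PSRT and SMC |
| Paragraph, sentence on the hold | Any triggered pause | PSRT or SMC |
| Paragraph, sentence on resumption | Any triggered pause | PSRT or SMC |

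That is two entries against two sentences. Four items are not counted because they answer other questions: rows 3 to 5 (whether to pause), footnote 3 (how to classify an event), the two later and/or phrases (recording a decision and informing regulators), and section 6.1.10.4 (individual participants, and whether to pause).

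**Step 2: does any text rank the two rules?** None in the available documents does. Nothing says that the table prevails, or that *or* means whichever body the row names. Section 15.1 does not help. After describing PSRT review of related AEs of grade 3 or above, it says: "The PSRT will decide by consensus whether AEs should also be reviewed by the SMC".

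**Step 3: do other safeguards make SMC agreement a condition of restarting the trial?**

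- *Related grade 4 SAE.* Section 15.2 stops enrolment until two or more SMC members have reviewed the event. This is a real condition, but it names enrolment only and does not reach grade 3.
- *Related grade 3 SAE.* Section 15.2 sends SAEs to the SMC within 2 working days, and section 15.3 says the SMC reviews them. Neither ties restart to the SMC's agreement.
- *Second related AE of grade 3 or 4, not serious.* Footnote 3 says "PSRT and SMC will determine whether the reported related AE (Grade 3 or 4) is a second occurrence". The SMC therefore helps establish that row 2 applies, but the footnote says nothing about resuming.
- *The affected participant.* Under section 6.1.10.4, item 1, a grade 3 or 4 AE related to romidepsin stops that person's further romidepsin, and both bodies review whether it may restart at a reduced dose. This does not cover other participants, or events related only to 3BNC117.

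**Result.** For trial-wide resumption, two situations remain where only the conflicting text of section 15.8 governs: a related grade 3 SAE, and a non-serious second related AE of grade 3 or 4.

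**The case against.** The strongest answer is that the two texts can be reconciled. The table is specific to each trigger; the paragraph is generic and must serve five rows, four naming both bodies and one naming the PSRT alone. *Or*, followed by two and/or phrases, could be shorthand for whichever body the row names. Rows 1 and 2 would then already need both. This may well be what was meant, and section 6.1.10.4 points the same way: it would be odd to require both bodies before one participant restarts romidepsin but only one before the whole trial restarts. The paragraph does not say so, however, and its literal wording permits the opposite.

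It is also fair to say that the SMC is already engaged. It receives SAEs promptly, reviews them, and helps classify row 2 events. A reader might infer that investigators could restart without the SMC knowing of the event, or that there is no external oversight of these events. The documents do not support either. What is unsettled is whether the SMC must agree.

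Two other inferences should be resisted. Because rows 1 and 2 mention only resuming enrolment, a reader might conclude that they leave infusions outside the pause; the opening of section 15.8 says that a pause covers both. A reader might also conclude that nobody is named to lift a pause called under rows 3 to 5; the paragraph names a body for any triggered pause, and those rows do not contradict it.

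Finally, the charter cited in section 15.8 was not available, and part of the text leading into the SMC provisions of section 15.2 was absent from the copy reviewed. Either could settle the matter.

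**Conclusion.** The inconsistency stands, limited to rows 1 and 2. Section 15.8 both requires and does not require the external SMC's agreement before enrolment and infusions resume after an automatic pause. Existing safeguards narrow the gap without closing it in the two situations identified above.

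This is a wording conflict in an operative safety rule and should be corrected. It has no bearing on sample size, power or type I error. Nor is it evidence that the sponsor intends investigators alone to lift these pauses. Confidence is high that the wording conflicts. That the conflict is unresolved rests on the assumption that neither the charter nor the missing SMC text resolves it.

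**What to change.** In both sentences of the paragraph under Table 1 (the one on holding and the one on resuming), replace *the PSRT or SMC* with *the body or bodies named in Table 1 (both the PSRT and the SMC for rows 1 and 2)*, and make clear that this applies to enrolment and infusions alike. If the charter covers resumption, check that it says the same.

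No new rules for rows 3 to 5 are needed, since the phrase carries over whichever bodies each row already names. The and/or wording on recording the decision and informing regulators can stay, and section 15.2 needs no change.

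The cost is a change of wording in one paragraph, with no effect on data collection or sample size. The small downside is that a pause may last slightly longer while the SMC responds.

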### **15.9 Futility Rule**

If 10 participants in a single group rebound before week 26 (2 weeks following ATI), additional participants from that group will not undergo ATI. In the case in which the futility rule is applied to both arms and only 10 participants undergo ATI in each arm, there will be 80% power to detect  $\geq 14$  days difference in time to viral rebound at 5% significance.

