## **3 Objectives and Rationale**

### **3.1 Introduction**

#### **3.1.1 Background**

Despite the major success of combination antiretroviral therapy (ART) in suppressing viral replication and preventing disease progression, HIV-1 infection persists and is not eliminated by available antiretroviral drugs. When ART is discontinued, viral rebound occurs within 2-3 weeks in most subjects (Davey et al., 1999) (Strategies for Management of Antiretroviral Therapy Study et al., 2006). Even in the context of suppressive ART, HIV infection is characterized by persistent low level HIV-1 viremia and immune activation and cell-associated HIV-1 remain relatively stable (Deeks et al., 2013). Studies have shown that intensified antiretroviral regimens do not affect low level viremia and do not result in lower levels of HIV-1 persistence (Markowitz et al., 2014; McMahon et al., 2010).

The primary barrier preventing HIV-1 eradication by ART is a pool of long-lived latently infected memory CD4+ T-cells (Chomont et al., 2009; Finzi et al., 1997). These cells harbor silent integrated proviral DNA capable of resuming HIV-1 expression upon activation (Archin et al., 2009; Bosque and Planelles, 2009; Finzi et al., 1999). In the inactive, resting state these cells cannot be recognized or eliminated by the immune system or antiretroviral drugs. Importantly, latently HIV-1 infected cells can be induced

to resume HIV-1 expression by latency reversing agents (LRAs) (Ylisastigui et al., 2004). This in turn could expose infected cells to immune-mediated recognition and killing.

Recent clinical trials have demonstrated proof-of-concept that the state of HIV-1 latency can be disrupted safely in patients on ART by a group of LRAs called histone deacetylase inhibitors (HDACi) (Archin et al., 2012; Elliott et al., 2014). However, the outcome of these trials plus an accumulating body of ex vivo research also suggest that, in the majority of patients, reactivation alone does not reduce the HIV-1 reservoir - possibly because of insufficient immune mediated killing of reactivated cells (Ho et al., 2013; Shan et al., 2012). This calls for combining LRAs with immune targeted interventions such as HIV-1-specific monoclonal antibodies.

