### 3.4 Primary Endpoint

- Days to viral rebound during ATI or days to reinitiation of ART in participants who restart ART before viral rebound. Viral rebound is defined as HIV-1 RNA  $\geq$  200 copies/mL on 2 consecutive measurements during ATI. If viral rebound occurs, the date of the first measurement of HIV-1 RNA  $\geq$  200 copies/mL will be defined as “date of viral rebound.”

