#### **6.1.7 ART interruption and re-initiation of combination ART**

ART regimen will be discontinued at week 24, 16 weeks after the second 3BNC117 infusion. ART will be discontinued for 12 weeks and if viral rebound does not occur, subjects can remain off ART with continued follow up.

At week 36, if a subject's HIV-1 VL remains undetectable, the subject will have the option to restart ART at that time or to continue weekly follow up through the end of the study (week 48). During the ATI, ART will be resumed if plasma HIV-1 RNA level  $\geq$  200 copies/ml in 2 consecutive measurements or if CD4+ count drops  $<$  350 cells/ $\mu$ l and the result is confirmed upon repeat measurement. In this case repeat measurements are performed at the next scheduled visit. If the HIV-1 RNA level is found to be  $\geq$  1000 copies/ml the subject will be contacted to return to clinic as soon as the result becomes available. Upon viral rebound, viral genotyping will be performed to determine if any resistance mutations are present. ART will also be reinitiated if the participant becomes pregnant, or if otherwise clinically indicated.

Subjects who experience viral rebound during the ATI will be followed on a modified schedule (Appendix B). These subjects will have study visits every 2 weeks until their HIV-1 VL is undetectable on 2 consecutive measurements. At that point, they will be followed every 8 weeks until the final visit at week 48.

Subjects' primary care physicians will be contacted when virologic rebound occurs and periodically throughout the study.

During ATI phase of the study subjects may be at increased risk of transmitting HIV to their partners and of HIV-1 superinfection from an HIV-infected partner. Therefore, subjects will be asked to use male or female condoms for the duration of ART interruption. In the event of a high-risk exposure to an HIV-infected partner, a subject may re-initiate ART as clinically indicated by his/her HIV primary care physician.

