### **8.2 Sample Size Considerations**

The sample size calculation is based on the primary analysis for the primary endpoint. We will compare days from day of ART interruption until day of viral rebound or day of reinitiation of ART without viral rebound in arm A to arm B (1:1 randomization) with the Wilcoxon-Mann-Whitney test. Given a standard deviation (SD) of 10 (days), enrolling 12 patients in each of the two arms, will have 80% power to detect  $\geq 13$  days difference in time to viral rebound at a 5% significance level ([Davey et al., 1999](#); [Hamlyn et al., 2012](#); [Hill et al., 2014](#)). The power calculation for this primary analysis was performed in G\*power using the minimum Asymptotic Relative Efficiency method.

To accommodate for dropouts, we aim to enroll 30 study subjects in the study (15 in each arm). A dropout rate of ~20% is anticipated.

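### Section 15.9 claims 80% power for a difference of 14 days or more in a case where every rebound time is under 14 days

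*Combined protocol and SAP*

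**What the plan says.** Section 15.9 sets the trigger: "If 10 participants in a single group rebound before week 26 (2 weeks following ATI), additional participants from that group will not undergo ATI". It then turns to the rule being met in both arms: "the futility rule is applied to both arms and only 10 participants undergo ATI in each arm, there will be 80% power". The effect attached to that power is 14 or more "days difference in time to viral rebound at 5% significance". The section gives no SD and does not say whether the test is one- or two-sided.

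The clock is fixed elsewhere:

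- Section 6.1.7: "ART regimen will be discontinued at week 24, 16 weeks after the second 3BNC117 infusion".
- Section 8.2 defines the primary comparison: "We will compare days from day of ART interruption until day of viral rebound or day of reinitiation of ART without viral rebound".
- Section 3.4 dates a rebound by the first of the two qualifying HIV-1 RNA measurements, not by the confirming one.
- Section 6.1.6 schedules weekly visits during the interruption.

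Section 8.2 also supplies the planning values: "Given a standard deviation (SD) of 10 (days), enrolling 12 patients in each of the two arms", 80% power for 13 days or more at 5%, and the Wilcoxon-Mann-Whitney test by the minimum asymptotic relative efficiency (ARE) method. Section 3.1.1 gives the expected course after stopping ART: "viral rebound occurs within 2-3 weeks in most subjects".

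**The concern.** Power is worked out before the data, from the sample size, the effect and the spread. Section 15.9 attaches it to a situation specified by the data. Once the trigger has been met in both arms and nobody beyond the tenth has interrupted ART, the range of the primary endpoint is known, and it is too narrow for either the effect or the SD behind the 80%.

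This is the protocol's only statement of what the primary comparison can show after interruptions stop early in both arms. If it stands, a non-significant 10 v 10 result could be reported as coming from an adequately powered test, when the conditions for that power were absent.

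**Working it through.** **Inputs.** From 15.9: 10 per arm, difference 14 days, 5% level. From 8.2: SD 10 days, Wilcoxon test, minimum ARE method. From 6.1.7 and 15.9: interruption at week 24 and cut-off at week 26, so (26 - 24) x 7 = 14 days. Assumed: the SD of 10 carries over to 15.9, and the test is two-sided.

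**1. The plan's own figure.** The effective sample size per arm is n x ARE, the noncentrality is (difference / SD) x sqrt(effective n / 2), and power comes from the noncentral t distribution.

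- Minimum ARE 0.864: effective n = 10 x 0.864 = 8.64; noncentrality = 1.4 x sqrt(4.32) = 2.91. Power is 77.7% with 2 x 8.64 - 2 = 15.28 degrees of freedom, or 78.6% with 18.
- ARE 0.955: 82.2%.
- Simulated exact Wilcoxon (reject if U <= 23 or U >= 77; actual level 4.3%): 80.0% to 80.3% in large runs.

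So 80% is reasonable for an unrestricted 10 v 10 comparison. The figure in 8.2 also reproduces: 12 per arm and 13 days give 80.1% by the minimum ARE method.

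**2. What the named case implies.** Ten interruptions and ten rebounds before week 26 in each arm mean that every participant who interrupted ART rebounded in time. All 20 times therefore lie from 0 to just under 14 days.

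- *Difference.* Two sets of values in that range must have means, and medians, less than 14 days apart.
- *SD.* The spread is largest with five values at 0 and five at 14. Each is then 7 from the mean, so SD = sqrt(10 x 49 / 9) = 7.38 days, against the 10 assumed.

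Neither result depends on a distribution.

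**3. Illustration of the power that remains.** Take normal times with SD 10 and a true 14-day shift, and restrict both arms to 0-14 days. The untruncated mean in arm B is an assumption, shown over a range (exact Wilcoxon, 100,000 runs each):

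| Assumed arm B mean (days) | Mean difference after restriction (days) | Wilcoxon rejects |
|---|---|---|
| 0 | 2.11 | 19.2% |
| 7 | 2.03 | 18.5% |
| 14 | 1.81 | 16.3% |
| 17.5 | 1.67 | 15.1% |
| 21 | 1.52 | 14.0% |

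Within-arm SDs after restriction are about 3 to 4 days. A separate run of the same model agreed to within half a percentage point.

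**4. Weekly visits.** The table treats time as continuous. On the actual schedule, a rebound dated before week 26 would almost always fall at the week 25 visit, about day 7. Nearly all 20 values would tie, and the test would have almost nothing to work on. If the week 26 visit is counted and times are grouped to days 7 and 14, the same model rejects in 9-16% of runs with a tie-corrected Wilcoxon and in 3-7% with Fisher's exact test.

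**5. How likely the case is.** Under the 14-day shift, the chance that the first ten in both arms all rebound before day 14 is the product of the two arms' probabilities raised to the tenth power. At an arm B mean of 7 days this is (0.758 x 0.242)^10, about 4 x 10^-8. At 14 days it is (0.5 x 0.081)^10, about 1 x 10^-14.

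**The case against.** The strongest reply is that the arithmetic is right. The sentence can be read as a general statement: the rule could leave as few as 10 per arm, and at that size the power for 14 days is 80%. Section 15.9 does not say that it conditions on the rebound times. The arithmetic point stands and is accepted above. The general reading does not fit the sentence, which opens by restricting itself to the rule having been met in both arms. If a general figure was meant, the text still needs to say so.

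A second reply is that the 14-19% rests on a continuous model that the visit schedule does not support, and on a loose use of section 3.1.1, where 2-3 weeks is an upper limit for most people and not a mean. An arm B mean of 0 days has no basis in the documents. All of this is fair, and the range should be read only as an illustration. But realistic visit timing lowers the power further, and step 2 needs no model.

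Reading the cut-off to include day 14 does not rescue the claim: one whole arm would have to rebound at day 0 and the other at day 14. More than 10 per arm might already be off ART when the trigger is met, and later times could then exist, but the sentence specifies only 10.

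Third, the case is so improbable under the planned effect that little hangs on it. That limits the consequence. It also means that, if the case did arise, it would itself be strong evidence against the assumed effect, and an assurance of 80% power to detect that effect would be misplaced.

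**Conclusion.** The concern holds. The 80% is a sound unconditional figure for 10 v 10, but it is stated for a case in which it cannot apply: all times are under 14 days, no 14-day difference can be observed, and the SD cannot exceed 7.4 days. These conclusions rest only on the week 24 and week 26 time points and on exactly 10 interruptions per arm. The size of the shortfall, roughly 14-19% in place of 80%, also depends on the normal model, the SD carried over from 8.2, a two-sided test and the assumed arm B mean. This is a correction to a stated figure that should be made; it is not a fault in the design.

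**What to change.** Delete the sentence in 15.9 that gives 80% power for 14 days and replace it with:

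> If the rule is met in both arms after 10 participants in each have interrupted ART, all rebound times are under 14 days, a between-arm difference of 14 days or more cannot be observed, and no power is claimed for this case.

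It would also be acceptable to keep the 80%, provided it is labelled as an unconditional calculation for 10 per arm (14-day shift, SD 10 days, two-sided 5%) and the text says that it does not apply once the rule has been met in both arms. Section 15.9 makes no power claim for the rule being met in one arm only, and none needs to be added.

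The cost is one sentence and a less favourable stated figure. The conduct of the futility rule, the primary test and the sample size in 8.2 stay as they are.
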